4.4.5 Management of stomatitis/oral mucositis/mouth ulcers

Stomatitis/oral mucositis/mouth ulcers are common toxicities associated with RAD001 and should be treated using local supportive care. Please note that investigators in earlier trials have described the oral toxicities associated with RAD001 as mouth ulcers, rather than mucositis or stomatitis. If your examination reveals mouth ulcers rather than a more general inflammation of the mouth, please classify the adverse event as such. Dose modification of RAD001 for stomatitis/oral mucositis/mouth ulcers is described in Section 4.4.4. Additionally, please follow the paradigm below for treatment of stomatitis/oral mucositis/mouth ulcers:

1. For mild toxicity (grade 1), use conservative measures such as non-alcoholic mouth wash or salt water (0.9%) mouth wash several times a day until resolution.
2. For more severe toxicity (grade 2 in which case patients have pain but are able to maintain adequate oral alimentation, or grade 3 in which case patients cannot maintain adequate oral alimentation), the suggested treatments are topical analgesic mouth treatments (i.e., local anesthetics such as, benzocaine, butyl aminobenzoate, tetracaine hydrochloride, menthol, or phenol) with or without topical corticosteroids, such as triamcinolone oral paste 0.1% (Kenalog in Orabase®).
3. Agents containing hydrogen peroxide, iodine, and thyme derivatives may tend to worsen mouth ulcers. It is preferable to avoid these agents.

Antifungal agents must be avoided unless a fungal infection is diagnosed. In particular, systemic imidazole antifungal agents (ketoconazole, fluconazole, itraconazole, etc.) should be avoided in all patients due to their strong inhibition of RAD001 metabolism, therefore leading to higher RAD001 exposures. Therefore, topical antifungal agents are preferred if an infection is diagnosed. Similarly, antiviral agents such as acyclovir should be avoided unless a viral infection is diagnosed.

4.4.6 Management of hyperlipidemia and hyperglycemia

Treatment of *hyperlipidemia* is recommended but not required as part of study therapy, and should take into account the patient's underlying condition and the relative risk/benefit ratio of treatment. Treatment of hyperlipidemia should take into account the pre-treatment status and dietary habits. For patients with grade 2 hypercholesterolemia (>300 mg/dL or 7.75 mmol/L) or grade 2 hypertriglyceridemia (>2.5 x upper normal limit) consideration should be given to treatment with a statin or appropriate lipid-lowering medication, in addition to diet. Patients should be monitored clinically and through serum biochemistry for the development of rhabdomyolysis and other adverse events as required in the product label/data sheets for HMG-CoA reductase inhibitors.

Note: Concomitant therapy with fibrates and an HMG-CoA reductase inhibitor is associated with an increased risk of a rare but serious skeletal muscle toxicity manifested by rhabdomyolysis, markedly elevated creatine kinase (CPK) levels and myoglobinuria, acute

renal failure and sometimes death. The risk versus benefit of using this therapy should be determined for individual patients based on their risk of cardiovascular complications of hyperlipidemia.

Grade 3 *hyperglycemia* has been observed in patients receiving RAD001 therapy. In almost all cases the affected patients had an abnormal fasting glucose at baseline. Based on this finding, we suggest that optimal glucose control should be achieved before starting a patient on RAD001 and should be monitored during RAD001 therapy. For patients who develop clinically significant hyperglycemia while on therapy, initiation of oral hypoglycemic or insulin therapy should be considered.

4.4.7 Management of non-infectious pneumonitis

Both asymptomatic radiological changes (grade 1) and symptomatic non-infectious pneumonitis (grade 2 = not interfering with activities of daily living or grade 3 = interfering with activities of daily living and oxygen indicated) have been noted in patients receiving RAD001 therapy. Non-infectious pneumonitis has been associated with RAD001 and other mTOR inhibitors (Atkins, 2004). In order to monitor for asymptomatic (grade 1) pulmonary infiltrates, a chest X-ray is required if a CT scan of chest is not used for bi-monthly disease evaluations. Additional chest X-rays/CT scans may be done, when clinically necessary. If non-infectious pneumonitis develops, consultation with a pulmonologist should be considered. Management of non-infectious pneumonitis suspected to be associated with RAD001 and dose modifications instructions are provided in Table 4.4.

Table 4.4 Management of non-infectious pneumonitis

Worst Grade Pneumonitis	Required Investigations	Management of Pneumonitis	Actions
Grade 1	CT scans with lung windows.	No specific therapy is required	Administer 100% of RAD001 and temozolomide doses.
Grade 2	CT scan with lung windows. Consider pulmonary function testing includes: spirometry, DLCO, and room air O ₂ saturation at rest. Repeat each subsequent Cycle until return to within normal limits. Consider a bronchoscopy.	Symptomatic only. Prescribe corticosteroids if cough is troublesome.	Discontinue study therapy until recovery to \leq grade 1. Study therapy may also be interrupted if symptoms are troublesome. If recovered, resume treatment with RAD001 and temozolomide at one lower dose level. Patients will be withdrawn from the study if they fail to recover to \leq grade 1 within 3 weeks.
Grade 3	CT scan with lung windows and pulmonary function testing includes: spirometry, DLCO, and room air O ₂ saturation at rest.; Repeat each subsequent Cycle until return to within normal limits. Bronchoscopy is	Prescribe corticosteroids if infective origin is ruled out. Taper as medically indicated.	Hold RAD001 and temozolomide until recovery to \leq grade 1. May restart RAD001 and temozolomide within 2 weeks at a reduced dose (by one level) if evidence of clinical benefit.

Worst Grade Pneumonitis	Required Investigations	Management of Pneumonitis	Actions
	recommended.		
Grade 4	CT scan with lung windows and required pulmonary function testing includes: spirometry, DLCO, and room air O ₂ saturation at rest. Repeat each subsequent Cycle until return to within normal limits. Bronchoscopy is recommended.	Prescribe corticosteroids if infective origin is ruled out. Taper as medically indicated.	Discontinue RAD001 and temozolomide.

* Patients will be removed from study if there is a repeat episode of pneumonitis or if pneumonitis does not resolve within 2 weeks.

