Metabolic changes (hyperlipidemia and hyperglycemia) may be observed during treatment with RAD001. Both events may be medically managed. Hyperlipidemia has been reported as an adverse reaction in 10% of patients although review of the laboratory values suggests that as many as a quarter of patients develop grade 1-2 hyperlipidemia on treatment, mostly hypercholesterolemia. Hyperglycemia has been reported as an adverse event in 7% of patients. Grade 3 hyperglycemia has been observed, especially in diabetics receiving RAD001 treatment. Therefore, patients with diabetes should have their blood glucose monitored carefully and their medications adjusted, as needed, to maintain adequate control of their blood glucose levels.

In Novartis-sponsored clinical trials, symptomatic non-infectious pneumonitis has been reported as a serious adverse event in less than 1% of patients out of approximately 1000 cancer patients treated with RAD001 as of April 30, 2006. This adverse event has been noted in the Investigators' Brochure (IB, Edition 4 dated November 11, 2005). Corticosteroids were often administered to the patients with symptomatic pneumonitis.

Novartis has recently received reports of low-grade non-infectious pneumonitis in cancer patients treated with RAD001. Most of these reports involve patients with no respiratory symptoms (CTC grade 1 pneumonitis: radiographic findings only) or mild severity (CTC grade 2: symptomatic, not interfering activities of daily living), and were from two investigator-sponsored (private IND) trials, as follows:

- In a study of patients with advanced renal cell carcinoma receiving 10 p.o. mg/day, 15/20 patients reviewed by an independent radiologist were noted to have lung infiltrates consistent with pneumonitis on routine chest CT scans performed to follow the patients' thoracic metastases.
- In a study of patients with advanced breast cancer, 7/18 patients treated with RAD001 10 mg/d and 2/16 patients treated with RAD001 70 mg/week, had findings consistent with pneumonitis. In this study, two patients, one on the daily RAD arm and one on the weekly RAD001 arm, developed severe (grade 3) pneumonitis that resolved after RAD001 was discontinued.

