4.3 Monitoring of suspected toxicities

Patients whose treatment is interrupted or permanently discontinued due to an adverse event or abnormal laboratory value suspected to be related to RAD001 or temozolomide must be followed at least weekly until the adverse event or abnormal laboratory resolves or returns to grade 1. If a patient requires a dose delay of > 21 days from the intended day of the next scheduled dose, then the patient must be discontinued from the study.

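### As printed, Table 4.4 gives two removal rules for Grade 2 pneumonitis: the row allows 3 weeks to recover, while the footnote, which names no grade, allows 2 weeks to resolve

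*Combined protocol and SAP*

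**What the plan says.** All the rules at issue are in Section 4.4.7 of the protocol, in Table 4.4 and its footnote.

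- **Grade 1 row:** "Administer 100% of RAD001 and temozolomide doses". The row gives no time limit and no removal rule.
- **Grade 2 row:** study therapy stops until recovery to grade 1 or less. Then: "If recovered, resume treatment with RAD001 and temozolomide at one lower dose level". For patients who do not recover: "Patients will be withdrawn from the study if they fail to recover to" at most "grade 1 within 3 weeks".
- **Grade 3 row:** both drugs are held until recovery to grade 1 or less, and then: "May restart RAD001 and temozolomide within 2 weeks at a reduced dose (by one level) if evidence of clinical benefit". This is the only row that mentions 2 weeks.
- **Footnote:** "Patients will be removed from study if there is a repeat episode of pneumonitis or if pneumonitis does not resolve within 2 weeks". It opens with an asterisk and names no grade.

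Two general rules surround the table. Section 4.3 takes a patient off study in this case: "If a patient requires a dose delay of > 21 days from the intended day of the next scheduled dose". Table 4.3 in Section 4.4.4 ends protocol therapy when a non-hematologic toxicity needs an interruption of more than 3 weeks, and it refers pneumonitis to Table 4.4.

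**The concern.** Two rules on the same page lead to opposite outcomes for one kind of patient. Under the row, a Grade 2 patient who takes between 2 and 3 weeks to reach grade 1 goes back on both drugs at a lower level. Under the footnote, that patient leaves the study. The recovery criteria also use different words: the row asks for grade 1 or less, and the footnote asks that the pneumonitis resolve.

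Appendix B provides for participating institutions outside the lead center, so different readings at different sites are foreseeable. What turns on the reading is, first, whether a patient with recent lung toxicity is re-exposed to the study drugs.

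Second, the reading may affect the primary endpoint. Restaging follows every two 28-day cycles (Section 5.1.2.3), and a response needs confirmation at least 4 weeks after it is first seen (Sections 6.1 and 6.3). The decision rule in Section 10.1 turns on small counts: 0 versus 1 response among 17 patients, and 2 versus 3 among 32. One would-be responder lost before confirmation could therefore matter.

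**Working it through.** The plan states no figure on this point to reproduce. The check compares the texts and then asks whether the size can be estimated.

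**1. The two clocks.** The row's limit is 3 weeks = 21 days and the footnote's is 2 weeks = 14 days, a difference of 7 days. Table 4.4 does not say when either clock starts. I assume both start on the same day.

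**2. Outcomes for a Grade 2 patient, if the footnote covers Grade 2.** Two meanings of 'resolve' are possible, so both are shown. The days are illustrative.

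| Course of the episode | Grade 2 row | Footnote, 'resolve' = grade 1 or less | Footnote, 'resolve' = complete disappearance |
|---|---|---|---|
| Grade 1 on day 10, infiltrates gone by day 14 | resumes | stays | stays |
| Grade 1 on day 10, infiltrates still present on day 14 | resumes | stays | removed |
| Grade 1 on day 18 | resumes | removed | removed |
| Not at grade 1 by day 21 | withdrawn | removed | removed |

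The third line (recovery on days 15 to 21) conflicts under either meaning. The second conflicts only if 'resolve' means complete disappearance.

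**3. Is it settled elsewhere?** No. Table 4.3 defers to Table 4.4 for pneumonitis. The general limits (more than 21 days in Section 4.3, more than 3 weeks in Table 4.3) agree with the row's 3 weeks but do not address the footnote.

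**4. Grade 1.** The row gives full doses. The footnote would remove a patient with persistent asymptomatic infiltrates only if it covers Grade 1 and 'resolve' means complete disappearance. The documents establish neither.

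**5. Timing against the primary endpoint.** First restaging comes after 2 × 28 = 56 days of treatment. Confirmation at least 28 days later gives 56 + 28 = 84 days. (Cohorts 1 and 2 add a 7-day observation period.) Removal before then may leave a response unseen or unconfirmed, although Section 5.1.3 does require a CT at completion of study.

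**6. Can the number affected be computed?** Section 1.3.2.1 gives three frequencies:

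- Renal cell study, 10 mg/day: "15/20 patients reviewed by an independent radiologist were noted to have lung infiltrates consistent with pneumonitis". 15/20 = 75.0%, exact 95% CI 51% to 91%.
- Breast cancer study, 10 mg/day: 7/18 = 38.9%, exact 95% CI 17% to 64%.
- Symptomatic pneumonitis reported as a serious adverse event: under 1% of about 1000 patients.

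The first two count findings of any grade, mostly with mild or no symptoms. The conflict concerns Grade 2 episodes that recover on days 15 to 21. That needs the share at Grade 2 and the distribution of recovery times, and the documents give neither. The number cannot be computed.

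**The case against.** The strongest reply concerns the footnote's scope. It begins with an asterisk, so it was probably attached to something in the table. No anchor is visible in the extracted text, where the table is broken across a page, and an anchor lost in extraction is not a fault of the plan. Only the Grade 3 row mentions 2 weeks, and the footnote would complete that row naturally. If it belongs there alone, the Grade 1 and Grade 2 conflicts largely fall away. This stands as a condition on the finding. It does not remove it, because the footnote's own words name no grade.

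A reader might infer that the footnote contradicts the Grade 1 row outright. The documents do not support that. The Grade 1 row states no removal rule, but it does not rule removal out either. Section 4.4.4 speaks of toxicities resolved to at least grade 1, and Section 5.1.3 of resolution to below Grade 2. On that usage Grade 1 pneumonitis already counts as resolved. Section 4.3 points the other way, since it lists resolving and returning to grade 1 as alternatives. A 2-week clock also fits poorly with the bi-monthly imaging used to look for Grade 1 infiltrates. The fair statement is that the reach to Grade 1 is unclear.

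A reader might also multiply 39% and 75% by the 32 Cohort 3 patients and conclude that about 12 to 24 are affected (32 × 7/18 = 12.4; 32 × 15/20 = 24). Those rates come from two small trials in other tumors, pool all grades, and apply only if Cohort 3 receives 10 mg/day, whereas it receives the MTD. They do not measure the conflict, and the same section gives the much lower figure for symptomatic serious events.

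Finally, removal does not by itself censor progression-free survival. Section 6.3 censors at the analysis cut-off or at further anti-cancer therapy and does not list removal for toxicity.

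**Conclusion.** The point holds in a narrow form. As printed, the Grade 2 row and the footnote give opposite outcomes for a Grade 2 patient who recovers to grade 1 on days 15 to 21, and no other section resolves the difference. This rests on two assumptions: that the footnote applies to Grade 2, as its unrestricted wording allows, and that both clocks start on the same day. If 'resolve' means complete disappearance, the conflict extends to patients who reach grade 1 earlier but still have infiltrates at 2 weeks. Whether persistent Grade 1 changes are caught is an open question of wording.

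The size is a 7-day difference between two stated limits. The number of patients in that window, and any effect on the response rate, cannot be estimated from the documents. The contradiction should be corrected because it governs removal and re-exposure after lung toxicity, and because a lost confirmation could matter in a design decided on very few responses. It does not show that the design or the primary analysis is unsound.

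**What to change.** The investigator and sponsor should reconcile the rows of Table 4.4 with its footnote. The revised table should state:

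- which grades the footnote covers, with its asterisk attached to those rows (first check where it sits in the source document);
- what 'resolve' means, and whether it differs from recovery to grade 1 or less;
- one time limit and one recovery criterion for each grade, with the day from which the limit is counted;
- for Grade 1, whether any removal rule applies.

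Which limit applies is for the investigator and sponsor to decide, and none is proposed here. The cost is a wording correction in one table, made by amendment. The sample size and the statistical analysis do not change.

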4.5 Treatment Plan

4.5.1 Investigational therapy

The investigational therapy used in the course of this study is RAD001 in combination with temozolomide. Study medication will be administered by the patients themselves. Patients are provided with a diary to document date, time, dose and any symptoms they experience while taking study medications. During the study, RAD001 will be administered orally as a once daily dose continuously from study day 1 until progression of disease or unacceptable toxicity. Patients in cohort 1 will receive RAD001 at a dose of 5 mg per day in combination with temozolomide 150 mg/m²/day on days 1-7 and 15-21 of each 28-day treatment cycle. Patients will be monitored for 7 days after their first cycle of therapy. They will not receive therapy during this observation period. Patients in cohort 2 will receive RAD001 at a dose of 10 mg per day in combination with temozolomide 150 mg/m²/day on days 1-7 and 15-21 of each 28-day treatment cycle. Patients will be monitored for 7 days after their first cycle of therapy. They will not receive therapy during this observation period. Patients in cohort 3 will receive RAD001 at the maximum tolerated dose in combination with temozolomide 150 mg/m²/day on days 1-7 and 15-21 of each 28-day treatment cycle.

Medication labels will comply with US legal requirements and be printed in English. They will supply no information about the patient. The storage conditions for study drug will be described on the medication label.

4.5.1.1 RAD001

RAD001 will be provided by Novartis. RAD001 is formulated as tablets for oral administration of 5mg strength. Tablets are blister-packed under aluminum foil in units of 10 tablets, which should be opened only at the time of administration as drug is both hygroscopic and light-sensitive.

RAD001 should be taken by the patient in a fasting state or with no more than a light fat-free meal. Vomited doses and missed doses should not be repeated. Dietary habits around the time of RAD001 intake should be as consistent as possible throughout the study.

4.5.1.2 RAD001 pharmacokinetics

The pharmacokinetic characteristics of RAD001 have been extensively investigated in the context of the drug's development as an immunosuppressant in solid organ transplantation where RAD001 was administered twice daily as a part of an immunosuppressant, multi-drug regimen consistently including cyclosporin A and glucocorticoids. Recent Phase I studies provide steady-state pharmacokinetics for both the weekly and daily schedules at varying dose levels in patients with advanced cancers.

RAD001 is rapidly absorbed after oral administration, with a median time to peak blood levels (t_{max}) of 1-2 hours postdose. The extent of absorption is estimated at above 11%. The area under the blood concentration-time curve (AUC) is dose-proportional over the dose range tested while maximum blood concentration C_{max} appears to plateau at dose levels higher than 20 mg. The terminal half-life in cancer patients averaged 30 hours, which is similar to that in healthy subjects. Inter-patient variability is moderate with the coefficient of variation (CV) of approximately 50%. A high-fat meal altered the absorption of RAD001 with 1.3 hour delay in t_{max} , a 60% reduction in C_{max} and a 16% reduction in AUC. In whole blood, approximately 80% of RAD001 is contained in red blood cells. Of the fraction of drug contained in plasma, 74% is protein-bound. The apparent distribution volume (V_z/F) after a single dose was 4.7 L/kg. RAD001 is eliminated by metabolism, mainly by hydroxylation, then excreted into the feces >80%.

RAD001 is mainly metabolized by CYP3A4 in the liver and to some extent in the intestinal wall. RAD001 is also a substrate of P-glycoprotein (P-gp). Therefore, absorption and subsequent elimination of systemically absorbed RAD001 may be influenced by medicinal products that interact with CYP3A4 and/or P-glycoprotein. *In vitro* studies showed that RAD001 is a competitive inhibitor of CYP3A4 and of CYP2D6 substrates, potentially increasing the concentrations of medicinal products eliminated by these enzymes. In two phase III clinical trials in patients following kidney transplantation, strong inhibitors of CYP3A4 (azoles, antifungals, cyclosporine, erythromycin) have been shown to reduce the clearance of RAD001 therapy thereby increasing RAD001 blood levels. Similarly, Rifampin, a strong inducer of CYP3A4, increases the clearance of RAD001 thereby reducing RAD001 blood levels. Caution should be exercised when co-administering RAD001 with CYP3A4 inhibitors or inducers.

Pharmacokinetic drug to drug interactions with cancer agents are being evaluated in ongoing phase Ib studies. Based on currently available results, gemcitabine (study 2101 part 2) and paclitaxel (study 2104) did not alter RAD001 pharmacokinetics to a clinically relevant extent whereas imatinib notably increased RAD001 exposure with a mean increase in AUC by a multiple of 3.7 for RAD001 administered weekly and two-fold for RAD001 administered daily (study 2206). Exposure to RAD001 in the presence of letrozole did not exceed that in monotherapy (study 2108). Co-administration of RAD001 did not influence pharmacokinetics of gemcitabine, imatinib or letrozole. Exposure to paclitaxel in the presence of RAD001 was slightly decreased (average by 23%).

RAD001 pharmacokinetics in transplant patients was investigated in special populations such as subjects with hepatic or renal impairment, various ethnic groups and pediatric renal transplant patients. In subjects with mild-moderate hepatic impairment, mean AUC to RAD001 is increased by 3-fold whilst renal impairment does not affect the pharmacokinetics

of RAD001. Age, weight (both over the adult range) and gender do not affect the pharmacokinetics of RAD001 to a clinically relevant extent. Also, pharmacokinetics does not alter in Japanese or Asian patients whereas black patients have 21% higher clearance compared to non-blacks. In children, the apparent clearance of RAD001 increases linearly with body surface. The clearance per square meter of body surface area is 12-fold higher compared with adult patients.

The pharmacokinetic parameters derived for RAD001 given weekly are summarized in Table 4.5.

Table 4-5 Steady-state RAD001 pharmacokinetics (weekly dosing)

Parameter	5 mg	10 mg	20 mg	30 mg	50 mg	70 mg
N	4	4	2	5	5	6
T _{max} (h)	1 (1-2)	1 (1)	1 (1)	2 (1-2)	1 (1-2)	1 (1)
C _{max} (ng/mL)	32 ± 15 □	69 ± 8	94 ± 0	88 ± 20	163 ± 63	174 ± 49
C _{max} /Dose	6.5 ± 3.1	6.9 ± 0.8	4.7 ± 0.0	2.9 ± 0.7	3.3 ± 1.2	2.5 ± 0.7
Ng/mL/mg						
AUC ^{ss} (ng-h/mL)	283 ± 48	573 ± 258	1001 ± 301	1798 ± 827	2621 ± 633	3615 ± 1497
AUC ^{ss} /Dose (ng-h/mL/mg)	57 ± 10	57 ± 27	50 ± 15	60 ± 28	52 ± 13	52 ± 21
t _{1/2} (h)	26 ± 3	38 ± 14	31 ± 12	37 ± 6	27 ± 7	26 ± 2

Values are median (range) for t_{max} and mean ± standard deviation for all others.

Reference: RAD001 Investigator's Brochure 2005

C_{max} was achieved by 1 to 2 hours post dose. While C_{max} rose in roughly dose proportional manner from 5 to 20 mg/week, it appeared to increase less than proportionally at higher doses.

